7.1 Primary Efficacy Analysis

The primary endpoint can be translated as a responder analysis where a subject will be classified as Responder if he/she achieves an IGA score of 0 (clear) or 1 (almost clear) at Week 8, considering a 2-point decrease from baseline. Patients who did not complete the study (i.e. subjects with an early termination visit at Week 8) will be classified as non-responder.

The comparison between groups for the primary endpoint will be done using a Cochran-Mantel-Haenszel (CMH) test where the site will be used as the stratification factor. A sensitivity analysis will also be conducted using a Fisher's exact without Site. Subgroup analyses will also be performed on responders vs. non responders (using CMH test stratified for site) for each subgroup of patients (Very Severe/Severe and Moderate), separately.

The primary efficacy analysis will be done using observed values. A supportive analysis will be conducted using the LOCF method. For subjects who did not complete the study, the last non-missing IGA results (including results collected during the early termination Week 8 visit) will be used.

The analyses will be done using the ITT population and will serve as the primary analysis while the analysis of the primary endpoint using the PP population will be used as a supportive analysis.

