By my signature, I agree to personally supervise the conduct of this study at my study site and to ensure its conduct is in compliance with the protocol, informed consent, Institutional Review Board (IRB)/Independent Ethics Committee (IEC) procedures, instructions from Innovaderm Research representatives, the Declaration of Helsinki, International Conference on Harmonization (ICH) Good Clinical Practices Guidelines, applicable Canadian regulations, U.S. federal regulations, and local regulations governing the conduct of clinical studies.

LIST OF ABBREVIATIONS

15 HETrE	15 hydroxyeicosatrienoic acid
AD	Atopic dermatitis
AE	Adverse Event/Adverse Experience
BMI	Body Mass Index
BSA	Body Surface Area
COX	Cyclooxygenase
CRF	Case Report Form
DGLA	Dihomo-gamma-linolenic acid
DLQI	Dermatology Life Quality Index
EASI	Eczema Area and Severity Index
ECRF	Electronic Case Report Form
EDC	Electronic Data Capture
ET	Early Termination
FDA	Food and Drug Administration
GCP	Good Clinical Practice
GLA	Gamma-linolenic acid
HBV	Hepatitis B Virus
HCV	Hepatitis C Virus
HIV	Human Immunodeficiency Virus
ICH	International Conference on Harmonization
IGA	Investigator's Global Assessment
IMP	Investigational medicinal product
ITT	Intent-to-treat
IRB	Institutional Review Board
IVRS	Interactive Voice Response System
IWRS	Interactive Web Response System
LOCF	Last observation carried forward
LPO	Lipoxygenase
MedDRA ©	Medical Dictionary for Regulatory Activities
PGE	Prostaglandine E
POEM	Patient Oriented Eczema Measure
PP	Per Protocol
PUVA	Psoralen and Ultra Violet A
REB	Research Ethics Board

SAE	Serious Adverse Event/Serious Adverse Experience
SOC	System Organ Classification
SCORAD	SCORing of Atopic Dermatitis
TEWL	Trans Epithelial Water Loss
UV, UVA, UVB	Ultra Violet (A or B)
VAS	Visual Analog Scale

SUMMARY

Title: **A Randomised, Double-blind, Placebo-Controlled, Phase II Study to Assess the Efficacy and Safety of orally administered DS107G to Patients with Moderate to Severe Atopic Dermatitis**

Phase: IIa

Population: Approximately 100 male or female subjects, aged 18 years or older, moderate to severe atopic dermatitis will be included in this study.

Number of Sites: Approximately 20 centers in Canada and US will participate in this study

Study Duration: 10 to 14 weeks including screening and follow-up

Hypothesis: DS107G is superior to placebo for improvement of IGA score in patients with moderate to severe atopic dermatitis.

Objectives:

Primary objective:

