Used drug boxes/blister packs will be stored safely until destruction and must be accounted for by the investigator. The study monitor will perform drug accountability for all study drug at the site and assist in returning study drug, including used and unused study drug to the Sponsor or designee. After verification of the drug accountability by the sponsor, the investigator will ensure proper destruction or return of the remaining study product.

Any study medication accidentally or deliberately destroyed will be accounted for. Any discrepancies between amounts dispensed and returned will be explained.

Drug inventory and accountability records will be maintained at each site as per GCP/ICH guidelines.

6.2.5 *Method of Assignment to Treatment*

Approximately 100 patients will be randomized into double-blind treatment groups in a 1:1 ratio by an Interactive Web Response System (IWRS) or Interactive Voice Response System (IVRS), as follows:

- Treatment group A: 2 grams DS107G (4 capsules)
- Treatment group B: 2 grams placebo capsules (4 capsules)

A randomization list permuted blocks and stratified by site will be generated by Dignity Sciences or its designee. The randomization schedule with study drug assignments will be generated prior to the start of the study and will be known only to the individuals responsible for labeling the study drug. The IVRS or IWRS will assign a study drug kit number to each subject and the contents will be based on the randomization code.

At the investigational site, each subject will be assigned a patient identifier number during screening that will be used on all patient documentation. The patient identifier number will contain the site number and the patient number assigned in numerical order at the screening visit (e.g.: 02-010 for the tenth patient screened at the site #02). Numbers will be assigned in ascending order starting with 001.

6.2.6 *Rationale for Selection and Timing of Doses in the Study*

Doses up to 4 g have been well tolerated in healthy subjects. The dose of 2 g has been selected as the tested dose in the current study based primarily on the pharmacokinetic results from the Phase I trial which suggested saturable skin levels of total DGLA with repeated oral dosing of greater than 2g per day.

In addition the following factors were considered:

- (a) there were less frequent transient gastrointestinal instances recorded at a dose of 2g compared to 4g daily

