3.4.3.5 Total and Free DGLA plasma levels, Total Fatty Profile and Interleukins levels

Total DGLA and free DGLA trough plasma levels will be measured at Baseline, week 4 and week 8. Total fatty profiles and interleukins levels will not be covered in this SAP.

4 Sample Size

The primary endpoint can be translated as a responder analysis where a subject will be classified as Responder if he/she achieves an IGA score of 0 (clear) or 1 (almost clear) at Week 8, considering a 2-point decrease from baseline. A sample size of 45 subjects will have a power of 80% to detect a statistically significant difference of 25% between responders from treated group and from the placebo group, based on a chi-square test and an alpha of 0.05. Based on the literature review, it is expected that the placebo could reach up to 7%, so the minimal proportion expected in the treated group should be at least 32%. Allowing for 10% drop-out, a total of 100 subjects should be enrolled in the study.

5 General Considerations

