5.4 Multi-centre Studies

The primary efficacy analysis will be performed with site included in the statistical model as a stratification factor. A sensitivity analysis will also be conducted without site. Analysis on the secondary efficacy endpoints will include information on site. Safety data will be presented with all study sites pooled. Safety analysis will be performed with data from all sites being pooled.

To obtain a sufficient and better-balanced number of subjects among study sites, pooling of study sites will be applied prior to performing the statistical inference and unblinding treatment. Sites without at least 5 subjects in the ITT population will be incorporated into pooled sites as follows:

- All such sites with less than 5 subjects will be ordered from the lowest to the highest in terms of number of ITT subjects. In case of ties, the ordering for tied sites will be determined according to the site identification number (from smallest to largest).
- Sites will be combined beginning at the smallest until the resulting pooled site contains at least 5 ITT subjects. The sites pooled in this way will be considered as a single site in the statistical analyses.
- The process described above will resume for the remaining sites not meeting the criterion of at least 5 subjects. If the final set of pooled site does not meet the criterion of at least 5 ITT subjects, the final set will be pooled with the preceding pooled site.

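### The severity-subgroup CMH tests use site strata pooled on the whole ITT population, so the smaller subgroup can lose much of its information to single-arm strata

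*SAP*

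**What the plan says.** SAP 7.1 compares week 8 responders between arms with a CMH test stratified by site, adds Fisher's exact test without site as a sensitivity analysis, and then continues: "Subgroup analyses will also be performed on responders vs. non responders (using CMH test stratified for site) for each subgroup of patients". The subgroups are baseline IGA 4 or 5 and baseline IGA 3, analysed separately.

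The strata come from SAP 5.4: "Sites without at least 5 subjects in the ITT population will be incorporated into pooled sites as follows". The count of 5 is taken over the whole ITT population. No rule re-pools sites once the data are split by severity.

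The Protocol Summary says "Approximately 20 centers in Canada and US will participate in this study". Protocol 6.2.5 says "Approximately 100 patients will be randomized into double-blind treatment groups in a 1:1 ratio", and describes the allocation as "A randomization list permuted blocks and stratified by site". Severity is not a randomisation factor, so arm balance within a site is not protected inside a severity subgroup.

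In mock Table 14.2.1.1.1 the Fisher p-value appears only for the overall comparison. Each severity block shows responder counts and percentages with the CMH p-value alone, and no difference or interval. Tables 14.2.1.1.2 to 14.2.1.1.4 follow the same layout.

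**The concern.** The pooling rule makes the strata workable for about 100 subjects, but the subgroup analysis divides each stratum again. With about 15 pooled strata the average is 100 / 15 = 6.7 subjects per stratum. A subgroup holding 20%, 30% or 40% of the trial then averages about 1.3, 2.0 or 2.7 subjects per stratum, and many strata will contain only one arm.

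The subgroup p-value would then rest on part of the subgroup and sometimes could not be computed. The table offers no unstratified test or interval beside it. A weak result could be taken to say more about treatment in that subgroup than the data allow.

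**Working it through.** **1. The plan's own figure.** SAP Section 4 and Protocol 14.1 give 7% on placebo, 32% on active, 45 subjects (read as per arm), 80% power, chi-square test and alpha 0.05.

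- Uncorrected: n = [1.96·√(2·0.195·0.805) + 0.8416·√(0.07·0.93 + 0.32·0.68)]² / 0.25² = 38.2, so 39 per arm.
- With continuity correction: (38.2/4)·[1 + √(1 + 4/(38.2·0.25))]² = 45.9, so 46 per arm.
- Power at 45 per arm: 79.1% with continuity correction, 86.2% without, 81.7% by exact enumeration of Fisher's test.
- Drop-out: 90 / 0.90 = 100.

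The overall sample size is reproduced to within one subject per arm. No subgroup power is stated.

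**2. Why single-arm strata drop out.** For stratum k with n subjects, n₁ active, n₀ placebo, m responders and a active responders, CMH sums a − n₁m/n over strata and divides the square by the sum of n₁n₀m(n − m)/[n²(n − 1)]. If n₀ = 0 then a = m and n₁m/n = m, so the difference and the variance term are both zero. The same holds if n₁ = 0, or if everyone or no one responds. If every stratum is like this, there is no p-value.

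**3. Simulation at the plan's rates.** From the documents: 100 subjects, 1:1, about 20 sites, blocks within site, the SAP 5.4 pooling rule, 7% versus 32%, 10% drop-outs counted as non-responders, two-sided 0.05. Assumed: equal-probability sites (about 15 strata after pooling), blocks of 4, severity independent of arm, the same rates in both subgroups, and the subgroup share.

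| Smaller subgroup, n | 20 | 30 | 40 |
|---|---|---|---|
| Subjects in single-arm strata | 49% | 32% | 20% |
| Power, CMH as planned | 6% | 20% | 34% |
| Power, Fisher's exact | 11% | 25% | 38% |
| Power, unstratified chi-square | 20% | 35% | 47% |
| Power, CMH re-pooled within subgroup | 17% | 31% | 42% |
| No CMH p-value as planned | 20% | 3% | 0.4% |

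Relative loss against chi-square: 1 − 6/20 = 70%, 1 − 20/35 = 43%, 1 − 34/47 = 28%. Against Fisher: 1 − 6/11 = 45%, 1 − 20/25 = 20%, 1 − 34/38 = 11%. In absolute terms this is 13 to 15 points against chi-square and 4 to 5 against Fisher.

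**4. Sensitivity to site layout** (separate runs without drop-outs, blocks of 4):

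| Layout | Loss vs chi-square at n = 20 / 30 / 40 |
|---|---|
| 20 sites of exactly 5 | 84% / 56% / 40% |
| 20 equal-rate sites | 72% / 45% / 28% |
| 20 sites, skewed enrolment (about 11 strata) | 55% / 34% / 19% |

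Across every layout tried, including 10 sites of 10, the loss at n = 20 to 40 runs from about 17% to 86%. Block sizes of 2, 4 and 6 make no material difference.

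**5. The other subgroup and the primary test.** The two subgroups partition the trial. At about 70 subjects CMH power is 67% against 72% for chi-square; at about 60 it is 59% against 67%. Without drop-outs, the relative loss at 70 to 80 subjects is 2% to 9% across layouts. At a 50/50 split each subgroup loses 12% to 26%. The primary CMH test on all 100 loses about 1 to 2 points.

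**6. Type I error.** With equal rates in both arms, rejection was at most about 3.5% for every option tried. No option, planned or proposed, inflates the error rate.

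**The case against.** The case for leaving the plan alone has force. Stratifying by site matches the randomisation, and Protocol version 2.2 deliberately replaced the chi-square test with CMH for the primary endpoint. SAP Section 11 lists the responder analysis by baseline IGA as additional to the protocol. Responder percentages by arm are printed in each severity block, so the observed effect stays visible. Against Fisher's test, which the SAP already uses, the gain is only 4 to 5 points.

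All of that stands, and it limits the size of the point. It does not answer the mechanism: the 5-subject rule is not applied where the subgroup tests are run.

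Three stronger readings are tempting, and the documents do not support them.

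- A reader might infer that both subgroups lose a third to three-quarters of their power. They share about 100 subjects, so both cannot be that small. The documents do not say which is smaller.
- A reader might infer that a non-significant result in the smaller subgroup would be the test's doing. The unstratified chi-square itself misses in 80% / 65% / 53% of trials, against 94% / 80% / 66% for CMH. At least four-fifths of the misses therefore come from small numbers (80/94 = 85%, 65/80 = 81%, 53/66 = 80%).
- A reader might infer that the primary analysis is compromised. It is almost unaffected.

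**Conclusion.** The point holds as a minor, conditional one. The site strata are not fit for a small severity subgroup. If that subgroup has about 20 to 40 subjects at about 20 equal-rate sites, about a half to a fifth of them contribute nothing. Power falls by 13 to 15 points against an unstratified chi-square, or 4 to 5 against Fisher's test. A missing p-value is a practical risk only near n = 20.

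The mechanism is certain. The size is not, because it depends on a severity split and site sizes that the documents do not give. Confidence in the magnitude is moderate. No stated power or error rate is breached; the case for change is that the remedy is cheap and uses subgroup data the planned test would discard.

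**What to change.** In SAP 7.1, and in the footnotes of Tables 14.2.1.1.1 to 14.2.1.1.4, choose one of these before unblinding:

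- Re-apply the SAP 5.4 rule within each severity subgroup, counting only that subgroup's subjects, and then run the site-stratified CMH. This keeps site in the test and recovers most of the loss (17% / 31% / 42% at n = 20 / 30 / 40).
- Test each subgroup without site strata, by the Fisher's exact test already in the SAP or by an unstratified chi-square.

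Under either option, add the responder difference between arms with its 95% CI for each subgroup. Keep the site-stratified CMH unchanged for the overall comparison.

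The cost is one SAP sentence, one footnote and one table row per subgroup. Re-pooling makes the strata coarser: at most 20/5 = 4, 30/5 = 6 or 40/5 = 8 of them. The unstratified option ignores the site stratification of the randomisation within the subgroups. Fisher's test also recovers less power than the other two choices.

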5.5 Multiple Testing

Since there are only 2 treatment groups involved in this study, no correction for multiplicity will be performed.

6 Summary of Study Data

All continuous variables will be summarised using the following descriptive statistics: n (non-missing sample size), mean, standard deviation (SD), median, inter-quartile range (25th and 75th percentiles), maximum, and minimum. The frequency and percentages (based on the non-missing sample size) of observed levels will be reported for all categorical measures.

In general, all data will be listed, sorted by treatment group, site and subject, and when appropriate by visit number within subject. All summary tables will be structured with a column for each treatment in the same order (DS107G, Placebo) and will be annotated with the total population size relevant to that table/treatment.

Day 0 is the first day of study medication. In the event that there is more than one value for a given assessment prior to the study drug start date, the value obtained closest to Day 0, before administration of study drug will be considered as the baseline value. The baseline value will be the value nearest to and before the first dose of the study medication.

All statistical tests will be two-sided and will be performed with a significant level of 0.05, unless otherwise specified.

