4 - Severe	n (%)	xx (xx.x)	xx (xx.x)	xx (xx.x)
5 - Very Severe	n (%)	xx (xx.x)	xx (xx.x)	xx (xx.x)
Week 8				
0 - Clear	n (%)	xx (xx.x)	xx (xx.x)	xx (xx.x)
1 - Almost Clear	n (%)	xx (xx.x)	xx (xx.x)	xx (xx.x)
2 - Mild	n (%)	xx (xx.x)	xx (xx.x)	xx (xx.x)
3 - Moderate	n (%)	xx (xx.x)	xx (xx.x)	xx (xx.x)
4 - Severe	n (%)	xx (xx.x)	xx (xx.x)	xx (xx.x)
5 - Very Severe	n (%)	xx (xx.x)	xx (xx.x)	xx (xx.x)
Responders ¹	n (%)	xx (xx.x)	xx (xx.x)	xx (xx.x)
Non-Responders	n (%)	xx (xx.x)	xx (xx.x)	xx (xx.x)
	p-value ²	xxxx		
	p-value ³	xxxx		
Week 8 - Very Severe/Severe⁴				
0 - Clear	n (%)	xx (xx.x)	xx (xx.x)	xx (xx.x)
1 - Almost Clear	n (%)	xx (xx.x)	xx (xx.x)	xx (xx.x)
2 - Mild	n (%)	xx (xx.x)	xx (xx.x)	xx (xx.x)
3 - Moderate	n (%)	xx (xx.x)	xx (xx.x)	xx (xx.x)
4 - Severe	n (%)	xx (xx.x)	xx (xx.x)	xx (xx.x)
5 - Very Severe	n (%)	xx (xx.x)	xx (xx.x)	xx (xx.x)
Responders ¹	n (%)	xx (xx.x)	xx (xx.x)	xx (xx.x)
Non-Responders	n (%)	xx (xx.x)	xx (xx.x)	xx (xx.x)
	p-value ²	xxxx		

Week 8 - Moderate⁴

0 - Clear	n (%)	xx (xx.x)	xx (xx.x)	xx (xx.x)
1 - Almost Clear	n (%)	xx (xx.x)	xx (xx.x)	xx (xx.x)
2 - Mild	n (%)	xx (xx.x)	xx (xx.x)	xx (xx.x)
3 - Moderate	n (%)	xx (xx.x)	xx (xx.x)	xx (xx.x)
4 - Severe	n (%)	xx (xx.x)	xx (xx.x)	xx (xx.x)
5 - Very Severe	n (%)	xx (xx.x)	xx (xx.x)	xx (xx.x)
Responders ¹	n (%)	xx (xx.x)	xx (xx.x)	xx (xx.x)
Non-Responders	n (%)	xx (xx.x)	xx (xx.x)	xx (xx.x)
	p-value ²	xxxx		

¹ Subject is classified as Responder if he/she achieves an IGA score of 0 (clear) or 1 (almost clear) at Week 8

² p-value from a Cochran-Mantel-Haenszel test with site included as a stratification factor

³ p-value from a Fisher Exact test (data from all sites combined)

⁴ IGA score at baseline visit.

Program: t14_2_1_1.SAS, Generated on DDMMYYYY HH:MM

Similar tables will be provided for

Table 14.2.1.1.2 Summary of Investigator's Global Assessment - Responder Analysis at Week 8 (Per Protocol Population)

Table 14.2.1.1.3 Summary of Investigator's Global Assessment - Responder Analysis at Week 8 (Intent-to-Treat Population) Supportive Analysis (LOCF)

Table 14.2.1.1.4 Summary of Investigator's Global Assessment - Responder Analysis at Week 8 (Per Protocol Population) Supportive Analysis (LOCF)

Table 14.2.1.2.1
Summary of Investigator's Global Assessment - Actual, Change and Percent Change from Baseline
(Intent-to-Treat Population)

Parameter	Statistic	Treatment Group		
		DS107G (N=XX)	Placebo (N=XX)	Total (N=XX)
IGA Score				
Baseline	n	xx	xx	xx
	Mean	xx.x	xx.x	xx.x

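### Separate subgroup tests by baseline severity in SAP 7.1 cannot show whether the treatment effect differs between moderate and severe patients

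*SAP*

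**What the plan says.** SAP 7.1 (Primary Efficacy Analysis) names one primary comparison, the site-stratified CMH test in the ITT population. It then adds: "Subgroup analyses will also be performed on responders vs. non responders (using CMH test stratified for site) for each subgroup of patients". The groups are Very Severe/Severe and Moderate.

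Mock Table 14.2.1.1.1 (SAP 13.1) prints one p-value per subgroup below the overall result. All carry the same footnote: "p-value from a Cochran-Mantel-Haenszel test with site included as a stratification factor". The layout is repeated in Tables 14.2.1.1.2 to 14.2.1.1.4 (PP, LOCF in ITT, LOCF in PP), which makes 2 × 4 = 8 subgroup p-values.

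No separate level is set for these tests, so the general rule in SAP section 6 applies: "All statistical tests will be two-sided and will be performed with a significant level of 0.05, unless otherwise specified". SAP 5.5 adds: "Since there are only 2 treatment groups involved in this study, no correction for multiplicity will be performed".

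Neither document plans a treatment-by-severity comparison or a confidence interval for the subgroup effects, and neither calls these results exploratory. SAP 7.3, the exploratory section, covers only TEWL. SAP section 11 lists among the additions to the protocol a responder analysis that controls for baseline IGA, but 7.1 contains separate tests and no adjusted model.

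**The concern.** The only reason to look by severity is to learn whether the effect depends on it. Two within-group p-values do not address that. Each asks whether the effect in one group differs from zero, and the answer depends heavily on how many patients the group holds. In a trial sized for one overall comparison, each part is underpowered, and the smaller part more so. A uniform effect can then easily print as significant in one group and not in the other.

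At stake is a mistaken conclusion that the drug helps only moderate, or only severe, disease. That could steer the choice of population for the next trial.

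**Working it through.** **Inputs.** Responder rates of 7% (placebo) and 32% (drug), 45 evaluable per arm, 100 enrolled (SAP section 4); 1:1 allocation; about 20 sites (protocol Summary); randomization stratified by site only (protocol 6.2.5); pooling of sites with fewer than 5 ITT subjects (SAP 5.4). Assumed, because not in the documents: a severe share of 20% to 50%, blocks of 4, sites of equal expected size.

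**1. The plan's own figure.** SAP section 4 states "A sample size of 45 subjects will have a power of 80% to detect a statistically significant difference of 25% between responders", "based on a chi-square test and an alpha of 0.05". The usual two-proportion formula gives 39 per arm without continuity correction and 46 with it. Exact power of the corrected chi-square at 45 per arm is 81.1%. Dropout: 90 / (1 − 0.10) = 100. The stated 45 (read as per arm) and 100 are reproduced to within rounding.

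**2. Power inside a subgroup, no site strata.** With n per arm and mean rate (0.07 + 0.32)/2 = 0.195:

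power = Φ{[0.25√n − 1.96√(2 × 0.195 × 0.805)] / √(0.07 × 0.93 + 0.32 × 0.68)} = Φ{(0.25√n − 1.098) / 0.532}

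At n = 45 this gives Φ(1.09) = 86%. At n = 22.5 (a 50/50 split) it gives Φ(0.165) = 56.5%.

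**3. Chance that exactly one test is significant.** With powers a and b in disjoint groups, this is a(1 − b) + b(1 − a).

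| Moderate/severe split | Power, moderate | Power, severe | Exactly one significant |
|---|---|---|---|
| 50/50 | 57% | 57% | 49% |
| 60/40 | 65% | 47% | 51% |
| 70/30 | 72% | 37% | 56% |
| 80/20 | 78% | 26% | 63% |

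For 70/30: 0.717 × 0.632 + 0.368 × 0.283 = 0.453 + 0.104 = 0.557.

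**4. The planned test.** Simulating the site-stratified CMH with N = 100, 20 sites and the SAP 5.4 pooling, with 7% against 32% in both groups:

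| Severe share | Exactly one significant | Both significant |
|---|---|---|
| 20% | 75% | 6% |
| 30% | 63% | 16% |
| 40% | 54% | 24% |
| 50% | 51% | 29% |

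The overall test succeeded in about 90% of these trials. Without site strata the discordance is about 47% to 66%, so the strata add to the problem but do not create it.

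**5. Sensitivity to the true effect.** With the planned CMH, still with equal effects, discordance is about 37% to 47% at a drug rate of 22% and about 38% to 84% at 42%. Without strata, at 45 per arm and a 50/50 split, step 3 gives 41% and 32%.

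**6. A direct comparison.** Take D = (drug − placebo in moderate) − (drug − placebo in severe), with variance equal to the sum of p(1 − p)/n over the four cells. At the design rates and 50 per arm:

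- 50/50 split: variance 0.2827/25 + 0.2827/25 = 0.0226, SE 0.150, 95% half-width 1.96 × 0.150 = 0.29.
- 80/20 split: variance 0.2827/40 + 0.2827/10 = 0.0353, SE 0.188, half-width 0.37.

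A Wald test of D = 0 is positive in about 4% to 5% of simulated trials when the effects are equal, and in about 30% to 44% when only moderate patients benefit. I could match those figures only with a small-sample adjustment (one half added to each responder and non-responder count). The unadjusted variance ran above 5% at every split tried.

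**The case against.** **The analysis is disclosed and secondary.** SAP 7.1 calls these subgroup analyses and introduces them after the single primary comparison. SAP section 11 reports an addition involving baseline IGA. Six of the eight p-values sit in PP or LOCF tables that the SAP calls supportive. All of this stands. A reader might infer that a significant subgroup could stand in for a failed primary test. No passage allows that; the gap is that none excludes it either.

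**The size is conditional.** This also stands. A reader might infer that the two p-values will normally disagree whatever the truth. They will not: unstratified simulation at 50 per arm puts discordance at 23% to 26% for a true drug rate of 15%, and at 22% for a rate of 42% with a 50/50 split. About half or more belongs to the design effect. Even the lowest of these figures is well above the roughly 5% error of a direct comparison.

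**Equal rates in both groups are doubtful.** Reaching IGA 1 takes a 2-point fall from baseline 3 but a 3-point fall from baseline 4. That is fair. The equal-effect case is a reference showing what the tests do when there is no difference to find; it is not a forecast.

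**Type I error is hardly touched.** With 7% in both arms, the chance that any of the overall and two subgroup tests falls below 0.05 is about 0.07 to 0.10. That is modest, and it counts tests to which the SAP attaches no claim. It is not the main reason for the change.

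**Homogeneity tests are too weak.** For Zelen's exact test this is right: it rejected in 1.2% to 1.6% of simulated trials with equal effects, and in only 7% to 15% when only moderate patients benefited. With 10 severe patients per arm, expected placebo responders are 10 × 0.07 = 0.7, too few for Breslow-Day. This argues for estimates with intervals, not for keeping the separate p-values.

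**Conclusion.** The point holds as a defect in how the subgroup question is analysed. The overall primary test, its alpha and the sample size are not affected. At the design effect, with equal benefit in both groups, the planned pair of tests gives a one-sided picture in about 51% to 75% of trials. These figures rest on an assumed severe share of 20% to 50%, blocks of 4 and about 20 sites of equal expected size, and they move with the true drug rate as shown. The pair of p-values therefore cannot show that the drug works in only one severity group. The documents do not support going further and saying that the trial's main conclusion is at risk or that the sponsor plans a subgroup claim. The change is worth making before database lock.

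**What to change.** In SAP 7.1 and Tables 14.2.1.1.1 to 14.2.1.1.4:

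1. Replace the two within-subgroup p-values with the responder risk difference and 95% CI in each severity group.
2. Add the difference between the two risk differences with its 95% CI and p-value, pooled over site. Name the variance formula, with a small-sample adjustment such as one half added to each cell. Do not use Zelen or Breslow-Day, for which the data are too sparse.
3. State that these results are exploratory and cannot support an efficacy claim if the overall ITT CMH test is not significant.
4. Make the SAP section 11 entry describe what 7.1 actually does.

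The cost is SAP wording and small edits to four mock tables, with no change to conduct or data collection. The sponsor gives up the subgroup p-values. The between-group comparison is imprecise (half-widths of about 29 to 37 points in step 6) and has low power, so the SAP should also say that a non-significant result is not proof of consistency.
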